#### 9.3.2 Diagnostic Performance

For each tracer method, calculate:

- Sensitivity =  $TP / (TP + FN) \times 100\%$
- Specificity =  $TN / (TN + FP) \times 100\%$
- Positive Predictive Value (PPV) =  $TP / (TP + FP) \times 100\%$
- Negative Predictive Value (NPV) =  $TN / (TN + FN) \times 100\%$
- 95% confidence intervals using Wilson score method

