## 2. INTRODUCTION AND BACKGROUND

### 2.1 Disease Background

Papillary thyroid carcinoma (PTC) is among the fastest-growing endocrine malignancies worldwide. Despite excellent overall prognosis, lymph node metastasis (LNM) remains a central clinical challenge. Even in patients classified as clinically node-negative (cN0) by routine preoperative ultrasonography and cross-sectional imaging, 30% to 80% may harbor occult LNM that is not detected before surgery.

This staging gap creates a significant clinical dilemma: extensive lymph node dissection may increase morbidity (including hypoparathyroidism and recurrent laryngeal nerve injury), while limited dissection risks leaving metastatic disease behind, potentially contributing to disease recurrence. A reliable intraoperative strategy that improves detection and risk stratification of occult nodal disease is urgently needed to support patient-specific, precision lymph node management in PTC.

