## 3. STUDY OBJECTIVES AND HYPOTHESES

### 3.1 Primary Objectives

1. To compare the sentinel lymph node detection rate among three tracer methods: ICG alone, CNs alone, and ICG+CNs dual-tracer combination.
2. To evaluate and compare the diagnostic performance (sensitivity, specificity, PPV, NPV) of each tracer method for predicting central lymph node metastasis.
3. To develop and validate deep learning models using multimodal features (spatiotemporal video features + clinical variables) for predicting second-echelon lymph node metastasis (SeLNM) and non-sentinel lymph node metastasis (NsLNM).

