## 4. STUDY DESIGN

### 4.1 Study Type and Design

This is a prospective, single-center, three-arm observational cohort study. Participants will be allocated to one of three groups based on the sentinel lymph node mapping technique used during their thyroid surgery.

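### NPV and PPV are to be compared between non-randomised tracer groups as crude within-group values, so a difference in metastasis prevalence can pass for a difference between tracers

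*Combined protocol and SAP*

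**What the plan says.** Section 3.1 lists as the second primary objective: "To evaluate and compare the diagnostic performance (sensitivity, specificity, PPV, NPV) of each tracer method for predicting central lymph node metastasis". Section 7.2 lists the same four measures as secondary outcomes.

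Section 4.1 describes a "prospective, single-center, three-arm observational cohort study" in which group membership is "based on the sentinel lymph node mapping technique used during their thyroid surgery". No randomisation, matching or stratification is described.

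Section 9.3.2 defines each measure from the true and false positives and negatives of one tracer group. The entry "Negative Predictive Value (NPV" is true negatives divided by all test negatives. The only inference named there is "95% confidence intervals using Wilson score method". Pairwise tests with a Bonferroni correction appear in 9.3.1, for the detection rate only. Section 9.2 compares baseline characteristics, but no adjusted analysis of tracer performance follows.

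On prevalence, section 5.4 plans with a single value of 50%. The background in 2.1 says that among cN0 patients "30% to 80% may harbor occult LNM that is not detected before surgery".

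**The concern.** Sensitivity and specificity condition on true nodal status, so they do not depend arithmetically on prevalence. NPV and PPV condition on the test result, so they do. If the groups differ in the proportion with central metastasis, their crude NPVs differ even when the tracers perform identically. Nothing in the allocation or the analysis makes that proportion equal.

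This is more than the usual confounding of a non-randomised comparison. It remains even if sensitivity and specificity are the same, and unbiased, in every group.

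NPV tells a reader how far a negative sentinel node can be trusted, which bears on the choice between extensive and limited dissection raised in 2.1. A case-mix difference reported as a tracer difference would mislead on that question.

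**Working it through.** **The plan's own figure.** The documents state no NPV or PPV, so there is none to reproduce. The total in 5.4 is derived from sensitivities and is not used here.

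**Inputs from the documents.** Sensitivity (se) 85% for the dual tracer and 50% for a single tracer, specificity (sp) 90% and planning prevalence (p) 50%, all from 5.4; 112 per group, from 4.2 and 5.4.

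**Assumptions.** The prevalence in each group; an unadjusted two-sided 5% two-proportion test of NPV; all 112 participants in each group entering the 2×2 table.

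**Formulas.**
- NPV = sp(1−p) / [sp(1−p) + (1−se)p]
- PPV = se·p / [se·p + (1−sp)(1−p)]

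**Step 1: identical tracers, se 85%, sp 90%.**
- p = 45%: NPV = 0.495/(0.495 + 0.0675) = 88.0%
- p = 55%: NPV = 0.405/(0.405 + 0.0825) = 83.1%
- p = 40%: NPV = 0.54/(0.54 + 0.06) = 90.0%
- p = 60%: NPV = 0.36/(0.36 + 0.09) = 80.0%

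PPV moves the other way: 0.34/(0.34 + 0.06) = 85.0% at p = 40% and 0.51/(0.51 + 0.04) = 92.7% at p = 60%.

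**Step 2: how often identical tracers would be declared different on NPV** (200,000 simulated pairs of groups of 112, sp 90%).

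| Prevalence | se 85% in both groups | se 50% in both groups |
|---|---|---|
| 50% vs 50% | 5% | 5% |
| 45% vs 55% | 12% | 22% |
| 40% vs 60% | 34% | 68% |

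At equal prevalence the test holds its level, so the excess comes from prevalence alone.

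**Step 3: reversal.** At equal specificity the worse tracer shows the higher NPV when the prevalence odds in the better tracer's group, divided by those in the other group, exceed (1−se_worse)/(1−se_better).
- 85% vs 50%: 0.50/0.15 = 3.33. With 50% prevalence in the single-tracer group, the dual-tracer group would need more than 76.9%.
- 85% vs 80%: 0.20/0.15 = 1.33. Against 50%, more than 57.1% is enough. At 60% vs 40% the better tracer shows 80.0% and the worse one 0.54/(0.54 + 0.08) = 87.1%.

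**Step 4: the planned contrast under imbalance.** At equal prevalence of 50%, NPV is 0.45/(0.45 + 0.075) = 85.7% vs 0.45/(0.45 + 0.25) = 64.3%, and the test rejects about 83% of the time. With 60% prevalence in the dual-tracer group and 40% in the single-tracer group, NPV is 80.0% vs 0.54/(0.54 + 0.20) = 73.0%. The order holds, but the gap falls from 21.4 to 7.0 points and rejection to about 14%.

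**Step 5: if specificity is 100%.** This would follow if a positive sentinel node on paraffin section itself counts as central metastasis. NPV at se 85% is still 90.9% at p = 40% and 81.6% at p = 60%. PPV is then 100% in every group.

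**The case against.** **No test of NPV is planned.** Section 9.3.2 asks for per-tracer estimates with intervals, so the rejection rates above belong to an assumed test. This stands. They show how misleading a crude comparison could be; they are not an error rate of the plan. But the objective says to compare, and crude values are all that 9.3.2 supplies for doing so.

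**The imbalance is assumed.** A reader might take the 30% to 80% in 2.1 as the spread to expect between these groups, and so infer that the dual tracer could easily rank below a single tracer. The documents do not support that. The range is general background on cN0 disease. The study has one centre, one enrolment period of April to October 2024 and one set of criteria. A 20-point gap is about three standard errors at 112 per group (0.20/√(2×0.25/112) = 0.20/0.067), so it would take real selection, which the documents neither show nor exclude. Reversing the 85% vs 50% contrast would take more than that.

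**Safeguards exist.** Sensitivity and specificity are reported alongside, the sample size rests on sensitivity, the primary hypothesis concerns detection rate, and 7.2 places PPV and NPV among the secondary outcomes. This lowers the weight of the point. It does not tell a reader of the NPV comparison what to discount.

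**NPV has no stated decision role.** No section makes NPV the basis for limiting dissection, and 6.3 gives every participant ipsilateral central dissection. The stake is how the results will be read, not how these participants are treated.

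**Conclusion.** The concern holds, at moderate weight. As written, the plan can report an NPV or PPV difference between tracers that is only a difference in prevalence, and it can hide or reverse a small true advantage. For identical tracers at 85% sensitivity and 90% specificity, the spurious NPV gap is 4.9 points at 45% vs 55% prevalence and 10.0 points at 40% vs 60%. These sizes depend on group prevalences that the plan does not give, and the corresponding rejection rates also depend on a test that it does not name.

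Two stronger readings should be set aside: that the plan carries a known false-positive rate for NPV, and that the planned 85% vs 50% contrast is likely to be reversed.

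**What to change.** Add to 9.3.2:
- Between-tracer conclusions rest on sensitivity and specificity.
- NPV and PPV are compared between tracers only at a common prevalence, namely the node-positive proportion on final histology pooled over the three groups. They are computed from each group's sensitivity and specificity by Bayes' rule, with bootstrap 95% intervals.
- Crude NPV and PPV are shown descriptively beside each group's prevalence, and no between-tracer conclusion is drawn from them.

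Check at a common prevalence of 50% and specificity 90%: two tracers with 85% sensitivity both give NPV 85.7%, and 85% vs 50% gives 85.7% vs 64.3%, in the right order.

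The cost is a few lines of SAP text and a short bootstrap, with no new data. The change has two limits. It does not remove case-mix bias in sensitivity itself. And if specificity is 100%, standardised NPV ranks the tracers exactly as sensitivity does, so it adds a readable scale but no new ranking information.

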## 9.4 Deep Learning Model Development

### 9.4.1 Model Architectures

Nine deep learning architectures will be developed and compared:

- Convolutional Neural Network (CNN)
- Long Short-Term Memory (LSTM)
- CNN + LSTM hybrid
- CNN + LSTM + Attention
- Transformer
- Crossformer
- 3D-CNN

- LSTM + Transformer hybrid
- LSTM + Crossformer hybrid

#### 9.4.2 Model Training

- Loss function: Binary cross-entropy
- Optimizer: Adam
- Learning rate: Adaptive with decay
- Regularization: Dropout and gradient clipping
- Data augmentation: Rotation, scaling, noise injection
- Class imbalance handling: Weighted loss function and oversampling

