### 3.2 Secondary Objectives

- To identify the optimal deep learning architecture for lymph node metastasis prediction.
- To determine the most important predictive features using SHAP analysis.
- To assess the clinical utility of AI-assisted intraoperative decision support.
- To evaluate safety outcomes including surgical complications and tracer-related adverse events.

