### 7.2 Secondary Outcomes

- Sensitivity, Specificity, PPV, NPV of each tracer method
- Deep learning model performance metrics (AUC, accuracy, F1 score, Brier score)
- Number of sentinel lymph nodes identified per participant
- Total number of lymph nodes retrieved
- Feature importance rankings from SHAP analysis

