### 8.3 Feature Extraction

Spatial Features (2,048 dimensions):

- Deep image features from EfficientNet-B5 pre-trained model
- Grayscale characteristics
- Shape and morphological features
- Hu moment descriptors

Temporal Features (20 dimensions):

- Frame-to-frame difference features (4 dimensions)
- Optical flow features (3 dimensions)
- Fluorescence time-series features (20 dimensions)

Dimensionality Reduction: Principal Component Analysis (PCA) to 32 dimensions

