#### 9.4.3 Model Validation

10-fold stratified cross-validation will be used:

- Data split: 90% training, 10% testing in each fold
- Stratification ensures balanced outcome distribution
- Performance metrics averaged across all folds
- Standard deviation calculated to assess stability

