### 9.6 Model Comparison

- DeLong test for comparing AUC values between models
- Probability-based model ranking approach (PMRA)
- Win-probability heatmaps
- Wald test p-value comparisons
- Decision curve analysis for clinical utility
- Calibration curves for reliability assessment
- Learning curves for overfitting assessment

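### Class balancing in section 9.4.2 can shift predicted risks off the real scale, and no recalibration is planned before Brier scores, calibration curves and decision curves

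*Combined protocol and SAP*

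**What the plan says.** Section 9.4.2 sets "Loss function: Binary cross-entropy" and, under the same heading, "Class imbalance handling: Weighted loss function and oversampling". It gives no class weights, no oversampling ratio and no order for the two steps.

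Three planned measures depend on the absolute level of predicted risk:
- Brier score: section 7.2 lists "Deep learning model performance metrics (AUC, accuracy, F1 score, Brier score" among the secondary outcomes, and section 9.5 repeats it.
- Calibration: section 9.6 plans "Calibration curves for reliability assessment".
- Net benefit: section 9.6 plans "Decision curve analysis for clinical utility". This serves the objective in section 3.2, "To assess the clinical utility of AI-assisted intraoperative decision support".

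Validation is by 10-fold stratified cross-validation (section 9.4.3: "Data split: 90% training, 10% testing in each fold"). Section 8.3 adds "Principal Component Analysis (PCA) to 32 dimensions" without saying on which data the components are fitted.

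The plan does not mention recalibration, correction for altered class proportions, or a calibration intercept or slope. It gives no expected prevalence for SeLNM or NsLNM. The only planning value, 50% in section 5.4, is for lymph node metastasis overall.

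**The concern.** Unweighted binary cross-entropy on unresampled data aims at the true risk. Reweighting or resampling the classes makes it aim at the risk in an artificial population with different class proportions. Ranking of patients can survive this, but the level of risk does not. Predicted risks come out too high when the outcome is rarer than 50% and too low when it is commoner.

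A useful model could then show poor calibration, a Brier score worse than giving every patient the prevalence, and net benefit below that of treating nobody. Decision curve analysis is the only analysis the plan labels as clinical utility, so a negative result there could be read as a failure of the video features when it came from the training recipe. The threshold-based metrics in section 9.5 (accuracy, F1, PPV, kappa) have no stated cut-off and would move as well.

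**Working it through.** The plan states no figure on this point, so there is none to reproduce. The check asks how far risks move and what that does to the planned measures.

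**Inputs from the plan.** Both imbalance methods and the loss (9.4.2); the measures (7.2, 9.5, 9.6); 112 patients in the modelled group (4.2); 50% prevalence of lymph node metastasis overall (5.4); a background range of 30% to 80% for occult metastasis (2.1).

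**Assumptions not in the plan.** AUC 0.80 with an equal-variance binormal score; a model that is well calibrated before balancing; full balancing at each step; test data left at natural prevalence; a decision threshold of 0.30 for illustration.

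**Size of the shift.** Let r = (1−p)/p.
- One method in full: predicted odds × r, that is, log-odds + ln r.
- Both in full, weights from the original class counts: odds × r², that is, log-odds + 2 ln r.
- Weights computed after full oversampling: the classes are already equal, the weights are about 1, and the shift is ln r once.

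At p = 0.20, r = 0.80/0.20 = 4 and ln r = 1.39. A patient with a true risk of 20% has odds of 0.25. One method gives 0.25 × 4 = 1, shown as 50%. Both give 0.25 × 16 = 4, shown as 80%. At p = 0.50, r = 1 and nothing moves.

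**Effect on the measures** (no balancing / one method / both in full):

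| Prevalence | Mean predicted risk | Brier score | Brier if all get the prevalence, p(1−p) | Net benefit at 0.30 |
|---|---|---|---|---|
| 20% | 0.20 / 0.42 / 0.67 | 0.126 / 0.18 / 0.37 | 0.160 | 0.061 / −0.007 / −0.11 |
| 30% | 0.30 / 0.45 / 0.60 | 0.158 / 0.183 / 0.258 | 0.210 | 0.13 / 0.11 / 0.05 |
| 40% | 0.40 / 0.47 / 0.55 | 0.177 / 0.183 / 0.201 | 0.240 | 0.23 / 0.22 / 0.21 |
| 50% | 0.50 in all three | 0.183 in all three | 0.250 | 0.34 in all three |

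Net benefit is the proportion of true positives minus the proportion of false positives × 0.30/0.70. Treating nobody scores zero. At 20% prevalence, treating everybody scores 0.20 − 0.80 × 0.30/0.70 = −0.143, so with both methods the model has moved most of the way towards flagging everyone.

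Above 50% the Brier scores mirror those below it (80% behaves as 20%), with risks pushed down.

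**Where the prevalence may lie.** By the definitions in 7.1.3 and 7.1.4, second-echelon nodes are non-sentinel nodes, so SeLNM cannot be commoner than NsLNM, nor NsLNM commoner than metastasis in any node. If the 50% in section 5.4 counts any node, it is a ceiling for both targets. If overall prevalence is nearer the top of the 30% to 80% range, the targets could exceed 50%.

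**The case against.** - **Doubling is not established.** This stands. It needs full oversampling and full weights from the original counts, and section 9.4.2 does not say so. Partial oversampling topped up by weights could also amount to one correction. One correction alone still takes net benefit below zero in the 20% example.
- **The only planning prevalence gives no effect.** True at 50%, but that value is not for the modelled outcomes, and a line on imbalance handling implies that some imbalance is expected.
- **A reader might infer that the measures themselves will be wrong.** The documents do not support this. On untouched test folds, Brier scores and calibration curves would correctly report a miscalibrated model. The risks are distorted, and net benefit is understated only relative to the same model recalibrated.
- **A reader might infer that ranking models by Brier score would reflect the resampling.** This does not follow. The nine architectures share one training recipe. Under a common shift at 25% prevalence, Brier scores for AUC 0.6, 0.7, 0.8 and 0.9 go from 0.18, 0.17, 0.14 and 0.10 without balancing to 0.42, 0.38, 0.30 and 0.21 with both methods. The order is unchanged. AUC, and the DeLong test on it, do not move under a pure shift.
- **A reader might infer leakage between folds.** The plan is silent on it. Oversampling sits under model training, and section 9.4.3 separates training from test data, so the natural reading is training data only. PCA uses no outcome labels. This calls for a clarifying sentence and is not a demonstrated error.
- **Patients are not affected.** This stands: section 6.3 says the predictions do not influence surgery. The stake is the reported performance and the clinical-utility objective.

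**Conclusion.** The point holds in conditional form. Followed as written, the plan puts predicted risks off the real scale whenever SeLNM or NsLNM is imbalanced, then assesses the models with measures that need that scale, with no step to restore it. How far depends on prevalence, class weights, oversampling ratio and order of steps, none of which is given. At AUC 0.80 with full balancing, the effect is large at 20% prevalence: with either one method or both, the Brier score is worse than predicting the prevalence for everyone. At 30% it is moderate, and only the double correction is worse than that benchmark. At 40% it is small, and at 50% absent.

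The figures rest on the assumed AUC and on a pure log-odds shift. A network that overfits a small training set need not follow that shift exactly. The change should be made because it is nearly free, but discrimination results do not depend on it.

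**What to change.** In sections 9.4.2 and 9.6:

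1. Recalibrate the outputs using training-fold data only, before Brier score, calibration curves, decision curves and any threshold-based metric. Either subtract the log-odds shift implied by the weights and oversampling ratio actually used, or update intercept and slope in inner folds. The first estimates nothing further. The second also handles departures from a pure shift but is fitted on about 112 × 0.9 ≈ 101 patients.
2. Compute these measures on test folds at natural prevalence.
3. If both imbalance methods are kept, compute the weights after oversampling so that the correction is not applied twice.
4. State the expected SeLNM and NsLNM prevalences, the oversampling ratio and the weights.
5. As a clarification only, state that oversampling and PCA are fitted inside each training fold after a split by patient.

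The cost is a few sentences in the SAP and a few lines of code, with no new data. Sensitivity or F1 at a default 0.5 threshold may fall.

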#### 9.4.3 Model Validation

10-fold stratified cross-validation will be used:

- Data split: 90% training, 10% testing in each fold
- Stratification ensures balanced outcome distribution
- Performance metrics averaged across all folds
- Standard deviation calculated to assess stability

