### 3.3 Hypotheses

Primary Hypothesis: The ICG+CNs dual-tracer combination will demonstrate superior sentinel lymph node detection rate compared to either tracer alone.

Secondary Hypothesis: Time-series fluorescence-flow signatures, combined with spatial structural cues and clinicopathological factors, will improve prediction of SeLNM and NsLNM compared with SLN status alone.

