### 4.2 Study Groups

Group 1 - ICG Group (n=112): Sentinel lymph node mapping using indocyanine green alone with near-infrared fluorescence imaging.

Group 2 - CNs Group (n=112): Sentinel lymph node mapping using carbon nanoparticles alone with visual identification.

Group 3 - ICG+CNs Group (n=112): Sentinel lymph node mapping using combined dual-tracer technique with both NIRF imaging and visual identification. This group will also undergo deep learning video analysis.

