### 9.5 Model Performance Metrics

The following metrics will be calculated for each model:

- Area Under the ROC Curve (AUC)
- Accuracy
- Sensitivity (Recall)
- Specificity
- Positive Predictive Value (Precision)
- Negative Predictive Value
- F1 Score
- False Positive Rate
- Lift
- Brier Score
- Kappa Coefficient
- Dice Coefficient

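### The best of nine architectures is chosen and scored on the same 112 patients, and the hypothesis that the models beat SLN status alone has no planned test

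*Combined protocol and SAP*

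**What the plan says.** Deep learning is confined to the ICG+CNs group of 112; section 4.2 says of it that "This group will also undergo deep learning video analysis". In section 9.4.1, "Nine deep learning architectures will be developed and compared". Section 3.2 lists as an objective "To identify the optimal deep learning architecture for lymph node metastasis prediction".

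Validation is described only in section 9.4.3. It is stratified 10-fold cross-validation with "Data split: 90% training, 10% testing in each fold" and "Performance metrics averaged across all folds", plus a standard deviation for stability. In section 9.5, "The following metrics will be calculated for each model". Section 9.6 plans a "DeLong test for comparing AUC values between models", a probability-based ranking, Wald p-values, and decision, calibration and learning curves.

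The hypothesis stated for the models (section 3.3) is that fluorescence-flow, spatial and clinicopathological information "will improve prediction of SeLNM and NsLNM compared with SLN status alone". Developing and validating the models is the third primary objective (section 3.1), and section 7.1.3 makes SeLNM their primary target.

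**The concern.** There are two gaps.

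- **Selection and scoring share the same data.** Each architecture's own out-of-fold figure is legitimate. The highest of nine such figures is not an unbiased estimate for the architecture that attained it, because part of its lead is chance. The plan has no other data on which to score the choice.
- **The model hypothesis is untested.** SLN status alone is neither among the nine architectures nor named in section 9.6.

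The gaps compound each other. If the winner's own figure were later set against SLN status, a gain would be shown too often when there is none. What is at stake is the answer to primary objective 3. Surgery is not affected, because section 6.3 keeps the predictions retrospective.

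A lesser point: sections 8.3 and 9.4.2 do not say whether PCA and oversampling are done inside each training part. That is silence, not shown leakage.

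**Working it through.** **Inputs from the documents.** 112 patients (4.2); nine architectures (9.4.1); ten folds (9.4.3), so 112/10 = 11.2 test patients per fold; two-sided alpha 0.05 (9.9); expected dual-tracer sensitivity 85% and specificity 90% (5.4). The plan states no model AUC, no correlation between models, no SeLNM or NsLNM prevalence (the 50% in 5.4 is for lymph node metastasis in general) and no power for the models. There is therefore no plan figure to reproduce.

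**Assumed ranges.** Prevalence 20-50%, true AUC 0.70-0.80, between-model score correlation ρ 0.3-0.9.

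**Step 1: is the hypothesis tested anywhere?**
- 9.4.1 lists nine architectures; none is SLN status alone.
- 9.6 compares models with each other.
- 9.3.2 describes each tracer method and makes no paired comparison with a model.
- SHAP (9.7) ranks features and does not compare a model with SLN status.
- SLN, SeLNM and NsLNM status are all collected (7.1.2-7.1.4, 8.1). SLN status is a listed clinical variable, so it probably enters the models, though the plan does not say so.

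The data exist; the test does not.

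**Step 2: optimism from choosing the best of nine.** Scores are binormal, AUC = Φ(d/√2), so d = 0.742 for AUC 0.70 and 1.190 for 0.80. Optimism is the mean of (best fold-averaged AUC − true AUC of that model), over 1,000 replicates.

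| Setting | Shared folds | Separate folds |
|---|---|---|
| Nine equal models, ρ 0.3-0.9 | 0.025 to 0.081 | 0.029 to 0.080 |
| One better by 0.05, ρ = 0.3 | 0.043 to 0.073 | 0.043 to 0.075 |
| One better by 0.05, ρ = 0.9 | 0.005 to 0.025 | 0.009 to 0.032 |

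The error is −0.003 to 0.003 for a pre-specified architecture (SD of its AUC 0.043-0.067) and −0.008 to 0.005 for nested selection.

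Hand check for equal models: optimism ≈ 1.485 × SD × √(1−ρ), where 1.485 is the expected maximum of nine standard normals. At the top, 1.485 × 0.067 × √0.7 = 0.083 (simulated 0.081). At the bottom, 1.485 × 0.043 × √0.1 = 0.020 (simulated 0.025). The approximation uses the score correlation in place of the correlation between AUC estimates.

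**Step 3: comparison with SLN status.** A binary predictor has AUC = (sensitivity + specificity)/2. Assumed 70/80% gives 0.75; 85/90% gives 0.875. Each of 600 replicates used 500 resamples of patients within outcome class, averaging AUC over folds that contain both classes. An unbiased 95% CI should lie wholly above zero in about 2.5% of replicates when there is no gain.

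| | CI above zero, no true gain | Coverage of 95% CI |
|---|---|---|
| Winner, ρ = 0.3 | 12-17% | not computed |
| Winner, ρ = 0.9 | 4-9% | not computed |
| Nested, ρ = 0.3 | 6.5-8.3% | 0.83-0.91 |
| Nested, ρ = 0.9 | 2.3-5.0% | 0.93-0.96 |
| Pre-specified | 1.0-3.2% | 0.92-0.98 |

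For a pre-specified architecture the CI half-width is 0.058-0.140. With a true gain of 0.05, its CI excludes zero in 12-37% of simulations. At least one fold lacked an outcome class in 73%, 29% and 6% of resamples at prevalence 20, 30 and 50%, so the averaging rule must be written down.

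**Step 4: models that are actually fitted.** Nine ridge models (SLN status plus 4-8 of 8 covariates), n = 112, 300 replicates. The winner reads 0.020-0.046 too high; pre-specified is within 0.007 of the truth and nested within 0.005. With no true gain, the CI lies above zero in 7-13% (winner), 0.7-3.0% (pre-specified) and 1.7-4.3% (nested). Coverage is 0.89-0.97 pre-specified and 0.90-0.96 nested. With 101 patients (112 × 0.90, assuming 90% have an identified SLN), coverage is 0.91-0.97 for both.

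**The case against.** **The winner will not be shown alone.** All nine are reported with an SD, calibration curves and learning curves, and the plan never says that the winner's figure is the headline. This is true, but none of these outputs removes the selection from that figure, and the plan offers no other estimate of the chosen model's performance.

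**The optimism may be small.** The architectures appear to share inputs and are trained on the same patients, so high correlation is plausible. At ρ = 0.9 with one better model, the bias is about 0.005-0.03, below the sampling SD of 0.04-0.07. This stands, and it is why the size is given only as a conditional range.

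**SLN status could be put into the DeLong test later, and 9.3.2 already reports SLN-based accuracy.** It could, but model, outcome and comparator would then be chosen after results are seen. Section 9.3.2 concerns tracer methods and supplies no paired contrast for SeLNM or NsLNM.

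**Nested selection is not a clean cure.** This stands. Its performance estimate is nearly unbiased, but its CI can fall to 83% coverage when models are weakly correlated. That favours pre-specification.

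**The hypothesis is labelled secondary, and power is low.** Both are true. It is nevertheless the hypothesis stated for the models, and the models are a primary objective. Low power calls for reporting an interval; it does not excuse omitting the comparison.

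**Conclusion.** The concern holds on both counts. That the model hypothesis has no planned test follows from the text and needs no assumption. That the figure for the architecture named optimal will tend to be too high follows from the design. Its size does not, and depends on assumed AUC, prevalence and correlation: 0.025-0.08 for nine equally good models, and between 0.005 and 0.075 if one is better by 0.05. Whether the models share folds changes this by at most 0.008. Used against SLN status, the winner would show a false gain in 4-17% of simulations, and a pre-specified architecture in 1-3%. The silence on PCA and oversampling is not needed for this conclusion. The plan should be changed before the models are analysed, because primary objective 3 depends on it.

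**What to change.** 1. **Section 9.4.3.** Name one primary architecture before any model result is seen, report its cross-validated figure as the main result, and label the ranking of the nine descriptive. If results have been seen, or the data are to choose, use nested cross-validation: choose inside each outer training part and report the outer-fold result as the performance of the selection procedure. Either way, do PCA, tuning and oversampling inside each training part.
2. **Section 9.6.** Add a paired comparison of that model or procedure with observed SLN status (0/1, final histology) in participants with an identified SLN, and report how many are left out. Test SeLNM first, and NsLNM only if SeLNM succeeds; another stated multiplicity rule would also serve. Compute both AUCs within outer test folds and average over folds containing both classes, which matches the fold averaging already planned. For the 95% CI, resample patients within outcome class, keep each patient's fold and prediction, and apply the same averaging rule. After nested selection, call the CI approximate, because it omits the variability of the choice, and state that it may under-cover.
3. **Only if the report will claim that video adds value,** also compare with a model of SLN status plus clinical variables without video, fitted and scored in the same folds.

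**Cost.** SAP wording and computing time; no new data. Pre-specification needs no runs beyond the planned 9 × 10 = 90 per outcome, but the named architecture may not be the best of the nine. Nested selection with an assumed 5-fold inner loop needs 9 × 10 × 5 = 450 inner runs, 10 outer refits and 90 for the descriptive ranking, 550 per outcome. Its result describes a procedure, since the choice can differ between folds. Tuning, and at least 10 runs for a no-video model, come on top. The reported AUC will probably be lower, and a modest true gain may not be shown.
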